Engaging serodiscordant couples in prevention and care as a dyad - When couples receive HIV counseling and testing together there is superior behavioral risk reduction than with individual VCT.¹⁴⁻¹⁶ Our experience in conducting large-scale VCT programs is that couples rarely test together, and often present sequentially for HIV testing, not in parallel. Those testing sequentially for HIV within a partnership frequently do not disclose their results to their partner. What is more, we believe that engaging the couple together in care will likely enhance retention and adherence.

Why Is This Study Important?

- Descriptive information on safety, acceptability, and uptake of couples-based self-testing is not available, despite the critical role sero-discordant couples play in the epidemic.
- It is critical that combination prevention programs identify lower cost methods of testing large numbers of people for HIV. Self-testing for HIV could be a vitally important innovation.
- Engaging couples in care as a dyad holds promise of improving entry, adherence, and retention in care programs.
- Despite its efficacy, PrEP has not been adopted widely. Understanding who would accept PrEP and how they would use it is critical to advancing integration of PrEP in combination prevention.
- Assessing the cost and efficiency of these interventions is critical for policy decisions.

PrEP for negative partners in a serodiscordant couple - despite strong evidence of the efficacy of PrEP in reducing incidence, its implementation has not been supported. Indeed, the original efficacy trial that showed the strongest effect was conducted among serodiscordant couples,¹⁷ and WHO has called for demonstration projects of PrEP with serodiscordant couples.

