Project Accept - This was a multisite community-based randomized controlled trial developed in direct response to our experiences in the VCT Efficacy Trial. Key goals were to test large percentages of the population, especially young people who have the highest incidence rate, and to do this within the communities where people live in order to destigmatize and normalize HIV testing. Project Accept had 5 sites: Kisarawe, Tanzania; Kwa Zulu Natal, South Africa; Soweto, South Africa; Mutoko, Zimbabwe; and Northern Thailand. The Project Accept intervention was designed to: (1) increase availability of VCT in community settings, (2) engage the community with mobilization activities, and (3) provide posttest psychosocial support. Intervention teams rotated through villages (activities were delivered in tents). The primary study endpoint was HIV incidence, measured in a post-intervention cross-sectional probability-based sample of all persons aged 18-32 years using an algorithm based on the BED assay, avidity index, and CD4+ T-cell count. Additional detailed information on the study design and assessment of the study design and endpoints can be found in the study protocol, which is registered with ClinicalTrials.Gov (identifier # NCT00203749). Project Accept has published 41 papers in peer-reviewed journals²⁶⁻⁶³ as of May 2014. The project has been highly successful in generating uptake of HIV testing and Post-Test Support Services. In a paper [name] recently published in Lancet Infectious Diseases⁴⁶ we reported that a significantly higher percentage of 16-32-year-olds were tested in intervention communities than in control communities. The mean difference in the proportion of clients receiving HIV testing between CBVCT and SVCT communities was 40.2% (95% CI 15.8–64.7; $p=0.019$). The overall estimated reduction in incidence in intervention vs. control communities was published in Lancet Global Health in 2014⁶⁴, and was 13.9% ($RR = 0.861$, 95% CI for $RR = 0.725$ – 1.023 ; $p = .08$). This trend was also seen in a preplanned subgroup analysis with a reduction in incidence for 25-32-year-olds of 25.4% ($RR = 0.746$, 95% CI for $RR = 0.536$ – 1.038 ; $p = .08$), and was significant with a 30.2% reduction in incidence ($RR = 0.698$, 95% CI for $RR = 0.543$ – 0.898 ; $p = .009$) for young women 25-32 years old.

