Enumeration of Household Members – When a household is approached for potential participation in the study, data collectors will explain the study, and with verbal consent of the head of household, establish if there are eligible couples within the household. Recruitment and Data Collection - Couples selected for inclusion will be invited to participate in the study. Couples are defined as two persons in an ongoing sexual relationship of at least 6-months, and each of these persons considers the other to be a “partner” in the relationship. To be eligible for participation, each individual has to be 18 years or older, live in the household regularly (thus, we are focused on cohabitating couples), and with no plans for moving from the area before the follow up period. Both members of the couple need to be aged 18 years or above, and at least one member of the couple must be aged 55 years or below. Additionally, each member of the couple must be willing to disclose their HIV status to their partner following self-testing, either facilitated by a counselor by the couples themselves. Before beginning the consent process, the interviewer will verify eligibility with the individual with respect to residency and age information. If the selected individual is not available during the household visit, the interviewer will be required to return to the household a minimum of two times (on different days/times of day) to locate the selected individual, request consent, and conduct the interview. Each member of eligible couples will be consented separately and in private, and consent of both members is required for entry into the study. Privacy will be ensured by having the consent and interview take place in a location where conversations cannot be overheard and the participant feels comfortable. If a couple declines to participate, they will be asked if they would be willing to tell us why. They will be consented for this process. At two weeks after leaving the self-testing kits with couples, data collectors shall return to study cohort members and repeat data collection (survey & blood for follow up interview). At this time, data collectors will collect any unused test kits and will also collect used test kits (sealable envelopes will be provided to participants to keep test kits after use). All collected test kits will be taken to the Study Center and kept in designated biohazard bins before being incinerated at the collaborating government health facility adjacent to the Study Center. At six months, a subset of participants will be approached to complete a follow up survey. The subset will consist of 50% of participants who were confirmed HIV positive (but no less than 20) and 5% of participants who tested negative (but no less than 10). For recruitment at the CTC, we will raise awareness about the study with existing CTC patients. If interested, these patients will be provided a card they can give to their partners to come and receive HIV testing through the study. The patients themselves will not have to retest for HIV since they are already receiving HIV-related care. The negative partner will receive HIV confirmatory testing at the Study Center. Serodiscordant couples in the area found through this recruitment strategy will be offered participation in the study. Similar eligibility criteria and definition of a “couple” used for the self-testing recruitment will also be used for the CTC-based recruitment (with the addition of residing near or within Kisarawe Ward). For CTC-based recruitment, written informed consent from both partners, completed individually and in private, will be required for entry into the study.

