
AIM 4 - We hypothesize that the program cost per client served associated with HIV testing and case detection for Dyadic-based Diagnosis, Care and Prevention (DDCP) will be substantially (~30%-50%) lower than for either clinic-based VCT or community based VCT; that HIV case detection will be more

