economically efficient (detect more cases at a lower cost); and, that DDCP will detect substantial more (GT ~ 80%) serodiscordant couples than the alternatives. For these analyses we will use standard procedures for estimation of the cost of interventions that adhere to the Panel on Cost-Effectiveness in Health and Medicine's guidelines.⁸⁰ This will include identification of the various types of resources consumed by the intervention, establishing a unit associated with each type of resource used, estimating the dollar value of each resource, calculating the number of units used, and multiplying the units of resources used by the dollar cost for each. These are summed to derive the cost of the intervention. Indirect costs will also be added to establish the gross cost. For each intervention and associated site we will estimate the total and average costs for the interventions. Startup costs will be annuitized over the life of the interventions using a standard annuity function. The discount rate utilized for the annuitization of one-time capital expenditures will be the same as that used in the overall analysis. We will estimate the full costs of the interventions, assuming no cost sharing, volunteer labor, or donated commodities. We will derive our cost estimates using a micro-costing methodology such that resource consumption is determined by identifying, measuring, and valuing all incremental costs needed to provide the interventions. These estimates will be compared with project budgets and reviewed with project staff to assure accuracy. These procedures were used for our costing of Project Accept interventions, and we have recently collected detailed costing estimates available for both clinic-based VCT and community-based VCT from the study area. In addition, we have highly detailed utilization data from Project Accept that specify associated rates of HIV case detection and rate of couple's HIV testing. These were recently published in Lancet Infectious Diseases.⁴⁶ Analysis for this aim involves direct comparison across program types (independent t-tests for mean differences, and non-parametric tests for counts) of differences in cost, efficiency, and number of serodiscordant couples detected.

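### Aim 4 compares case yield, cost per case and serodiscordant couples detected across programmes with different eligibility, unadjusted, so differences cannot be credited to the testing method

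*Combined protocol and SAP*

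**What the plan says.** The AIM 4 paragraph (section D, Evaluation of Specific Aims & Associated Hypotheses) makes three separate predictions:

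- The "program cost per client served associated with HIV testing and case detection" will be "substantially (~30%-50%) lower than for either clinic-based VCT or community based VCT".
- Case detection will be more efficient, meaning more cases for less money. No size is given.
- "DDCP will detect substantial more (GT ~ 80%) serodiscordant couples than the alternatives". No denominator is given.

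The comparator figures come from "highly detailed utilization data from Project Accept that specify associated rates of HIV case detection" and of couple testing. The analysis contrasts the programme types directly, with t-tests for means and non-parametric tests for counts. No restriction, matching or standardisation is mentioned.

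The two populations are described as follows.

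- **DDCP** (section D, Recruitment and Data Collection): cohabiting couples together for at least six months. "Both members of the couple need to be aged 18 years or above, and at least one member of the couple must be aged 55" or below.
- **Project Accept** (section C): a programme meant to test much of the population, young people in particular. One reported result is that "a significantly higher percentage of 16-32-year-olds were tested in intervention communities than in control communities". No partnership criterion is stated.

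The box on why there is no control group relies on Project Accept for the cost comparison. It offers only the shared area and recent collection as grounds for comparability.

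**The concern.** Project Accept stands in for a control group in Aim 4, but the two programmes did not test the same kind of people. DDCP's entry rules fix partnership status and set age limits before any kit is handed out. Positivity, and the chance that a tested person belongs to a couple whose joint status becomes known, both depend on those features. An unadjusted contrast would therefore show a difference even if household self-testing and standard VCT performed identically.

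This matters because the Innovation list in section B presents the Project Accept comparison as one between competing testing methods, and presents self-testing as a way to lower testing cost. A reader deciding whether to fund self-testing would take a lower cost per case, or a larger number of discordant couples found, as a property of the method. Part of either result, possibly all of it, could come from eligibility.

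**Working it through.** **The plan's own figure.** The 30-50% saving cannot be reproduced. The documents give no unit cost, positivity, standard deviation or sample size calculation for Aim 4.

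**Where eligibility enters.** Let C be total programme cost, N clients served and p the proportion positive.

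- Cost per client served = C/N. Neither positivity nor couple status appears in it.
- Cost per case detected = (C/N)/p.

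**Cost per case.** Hold C/N equal in the two programmes and let R = DDCP positivity / comparator positivity. The saving per case is 1 - 1/R. R is an assumption, shown as a range:

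| R | Cost per case, DDCP vs comparator | Cost per client served |
|---|---|---|
| 0.8 | 25% higher | no change |
| 1.0 | equal | no change |
| 1.2 | 17% lower | no change |
| 1.43 | 30% lower | no change |
| 1.5 | 33% lower | no change |
| 2.0 | 50% lower | no change |

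**The same on the planned yield.** Precision of Estimates and Statistical Power (AIM 1) expects 60 discordant couples from 442, or from up to 1000. Each has one positive partner, so positivity among individuals is at least 60/884 = 6.8%, or 60/2000 = 3.0%, if everyone enrolled is tested.

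- From 6.8%: comparator positivity of 6.8% × 0.70 = 4.8% gives a 30% lower cost per case, and 6.8% × 0.50 = 3.4% gives 50% lower.
- From 3.0%: the corresponding values are 2.1% and 1.5%.

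A significance test does not guard against this. Section C reports 7,196 Project Accept tests in the district. I treated tests as independent clients and used a two-sided 5% test of two proportions as a stand-in for the plan's tests. Differences of these sizes would be significant with power 0.72 and 0.99 (442 couples), or 0.65 and 0.98 (1000 couples).

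**Serodiscordant couples.** The hypothesis names no denominator, so take couples detected per client tested. Let d be the proportion of tested couples that are discordant, equal in both programmes, and q the share of comparator clients tested as couples.

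- DDCP: d/2 per client, since every client is half of a couple.
- Comparator: q × d/2 per client.
- Excess = 1/q - 1. It is above 80% whenever q is below 1/1.8 = 55.6%.

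The documents give no value for q. Assumed values give +100% at q = 50%, +233% at 30% and +900% at 10%. Section B says of the team's earlier large VCT programmes that "couples rarely test together, and often present sequentially for HIV testing, not in parallel", which points to a q well below 56%.

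**Like-for-like check.** If the comparator had the same eligibility as DDCP, and positivity then matched, R = 1 and q = 1. The contribution of eligibility to both outcomes would be 0%.

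**The case against.** The strongest reply is that targeting couples is the intervention. Specific aim 4(b) compares DDCP as a whole with clinic-based and mobile VCT, and the background argues for directing services to those most likely to transmit or acquire HIV. On that view a higher yield from choosing couples is part of the effect sought, and the study calls itself exploratory. This stands as a reason to keep the whole-programme contrast. It does not support reading that contrast as a comparison of testing methods, which is how the Innovation list frames it.

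A second reply is that the comparator population is not fully known. This also stands. The 16-32 range belongs to one reported testing result; it is not a stated limit on who was served. The lack of a partnership restriction is inferred from silence. The plan says couple-testing rates exist, so some testing as couples was recorded. The cited source does not settle the matter: both places cite reference 46 as a Lancet Infectious Diseases paper, but entry 46 in the list is a surveillance pilot in another journal.

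A third reply concerns feasibility. Section C confirms detailed individual utilization data on all clients, but not that age, sex or couple status was recorded, or that partners who tested at different times can be linked. Restricting both programmes to ages 18-32 would split couples with one older partner. Those limits shape the fix below.

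**Conclusion.** The concern holds for case yield, cost per case and serodiscordant couples detected. As planned, differences in these outcomes reflect eligibility and testing method together and cannot be assigned to the method.

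- **Serodiscordant couples** are the clearest case. On a per-client basis, and assuming equal discordance per couple, the prediction of more than 80% is met by eligibility alone if fewer than about 56% of comparator clients test as couples. The plan's own background makes that likely.
- **Cost per case**: size and direction are unknown. Positivity ratios of 1.43 to 2.0 would give 30% to 50% lower cost per case at equal cost per client. A ratio of 0.8 would make DDCP look 25% more expensive.

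A reader might go further and infer that eligibility alone can produce the hypothesised 30-50% saving. The documents do not support that: the saving is stated for cost per client served, which case mix does not mechanically change. Nor do they support saying that Project Accept served only people aged 16-32, or that the bias must favour DDCP.

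**What to change.** In the AIM 4 analysis text:

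1. Report cost per client served and cost per case detected as separate outcomes, and tie the 30-50% hypothesis to the first.
2. Keep the whole-programme comparison, stating that it reflects targeting and testing method together.
3. Beside it, prespecify a comparison of case yield and cost per case in which the Project Accept individual utilization records are standardised to DDCP's age and sex distribution, over the ages both programmes cover. A simple rule for cost per case is programme cost per client divided by standardised positivity. It assumes that cost per client does not vary with age or sex.
4. Report serodiscordant couples per client tested and, where the records identify couples, per couple tested.
5. Draw conclusions about self-testing as a method only from the standardised comparison, noting that age and sex standardisation leaves any partnership difference in place.
6. Correct the citation for the Project Accept rates.

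The cost is plan wording and re-analysis of records the team says it holds. The price is wider uncertainty, and dependence on age, sex and couple status having been recorded. If they were not, the plan should say so and limit its claim to the whole-programme contrast.

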The Triage Project - In Kisarawe district we have recently initiated a two-arm Phase II community randomized controlled trial (N=355 per arm) in two matched rural communities (different communities from those proposed herein). The primary endpoint is HIV and STI incidence. The intervention components include: community mobilization, community-based VCT at a community prevention center, enhanced counseling for high risk and HIV-infected clients, and incentives for uptake of VCT by sex partners of high risk and HIV-infected clients. For clients who test positive for HIV there is posttest psychosocial support, income generation activities, assisted and active referral to treatment, and adherence support for treatment. Formative work has y been completed, and the study plans is currently enrolling participants.

Our research experience, infrastructure and staff capacity in Tanzania are excellent. Our team has the following accomplishments with Project Accept: (1) created detailed physical maps of this rural district, (2) mapped every household in the entire district with a population of approximately 160,000 using GPS technology at baseline and again recently at follow up, (3) conducted 3,065 baseline field interviews, (2) 463 serial qualitative interviews over 30-months, (3) 20 key informant qualitative interviews, (5) 7,196 HIV tests with counseling, (4) 9,772 post test support visits, (5) 4,197 community mobilization activities and events reaching 103,870 persons, and (6) trained and supported 74 part time community outreach volunteers. For our recent post-intervention assessment, we have had the following success: (1) response rate for household enumeration of 98.4%, (2) consent rate for individual interviews of 96.8%, (3) consent rate for post-intervention blood collection in household of 82.7%, and (4) completed survey response of 96.1%. We have also conducted detailed costing of all intervention components at two time points, collected detailed individual intervention utilization data on all clients, held regular community advisory board meetings, and have had regular external intervention quality control assessments.

How will we do the work?

- Enumerate, and enroll approximately 442 (and up to 1000) couples aged 18+. Obtain individual informed consent.
- Baseline interview administered and biometric data (fingerprint) collected.

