measures were developed for Project Accept and will be used in this study. We will inquire about behavioral intention to seek VCT, attitudes (fears, worries, resolve, anxiety), self-efficacy to seek VCT, perceptions of abilities to overcome barriers, norms regarding VCT in the community, and perceptions of support for intentions. Items were constructed, tested for meaning in pilot studies, revised and translated/back-translated for meaning in Project Accept. In Project Accept these measures resulted in an alpha of 0.81 at baseline. **(5) Discussions about HIV** In the NIMH Collaborative HIV/STD Prevention Trial baseline questionnaire, questions were developed for a five-country community-randomized trial (Zimbabwe, Peru, China, India, and Russia) to capture key elements of community conversations about HIV/AIDS and the frequency of discussion with specific individuals (spouse, family, friends, key opinion leaders); we adapted these items for use. In Project Accept these measures resulted in an alpha of 0.76 at baseline. **(6) Disclosure of HIV status** will be measured as it was in earlier VCT research in Africa.⁷⁶ The instrument asks about the disclosure of serostatus to spouses, sexual partners, immediate family, other relatives, friends, religious leaders, health care professionals, and employers. The proportion of participants reporting each disclosure will be calculated after eliminating those who say the disclosure was not applicable to them. In Project Accept these measures resulted in an alpha of 0.83 at baseline. **(7) HIV-related negative life events** will be measured as they were in prior VCT research in Africa⁷⁶. Negative HIV-related life events include breakup of a marriage or sexual relationship, physical abuse by a sexual partner, neglect by family, being disowned by family, rejection by peers, and being discriminated against by health care providers or employers. The proportion of participants reporting each life event is calculated after eliminating those who say the life event was not applicable to them. In Project Accept these measures resulted in an alpha of 0.74 at baseline. **(8) Safety Related to Intervention** measures will assess specifically whether any adverse events (such as those listed in item 7 above) were experienced as an outcome of receiving each specific intervention component from the study. We will especially assess consequences of HIV self-testing, disclosure of HIV test results, accessing treatment, and PrEP utilization. We will also ask whether there was any coercion, pressure, or sanction for experience for clients to receive services and the source of each. These detailed questions will be added to our utilization data collection forms for each service assessing negative life events experienced from previous services received from the project. **(9) Potential for Misrepresentation** will also be assessed with regard to whether clients indicate higher risk behaviors than are true. We will do this by comparing data across couples, and over time to establish whether there are inconsistent results emerging. **(10) Cost** - The PI has significant experience with costing and cost-effectiveness analysis and led the costing component of the previous multi-site study. Cost data will include a range of costs for each item, with high, low, and average costs recorded. Data to be collected include: (1) Conversion rate of local currency to US dollars at 6-month intervals over the life of the project; (2) buying power of the currency at the beginning, midpoint, and end of the project based on the World Bank's Purchasing Power Parity Index; (3) costs of all commodities used in the intervention; (4) labor costs for intervention workers; (5) promotional and advertising costs; (6) average time clients spent with intervention; (7) rent; (8) maintenance; (9) incentives to participants; (10) volunteer activities; (11) user fees; (12) value of donated goods and services; and (13) other relevant costs. An annuity function will be applied to startup costs and they will be distributed over the life of the intervention. Time preference will be taken into account by applying discounting to future benefits at 0%, 5% and 7% as recommended by the US Panel on Cost-Effectiveness in Health and Medicine⁸⁰. **(12) Clinical** - for serodiscordant couples we will collect from the CTC: (1) date, time and reason for clinic visit, (2) results of CD4 and viral load tests (if any), (3) any reported medication side-effects, (4) medications prescribed, (5) pick up time and date of prescriptions, (6) HIV test results, (7) change or stop events for medications and associated reasons noted in record. These same results will be available in blinded format for other clients enrolled in the CTC and will be collected for comparison. In addition, for those in the cohort we shall conduct a HIV test at the follow up interview with counseling and referrals for care. For HIV positive members of serodiscordant couples followed in the cohort we will also collect blood for a viral load test at the time of the final interview to assess viral suppression.

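### Aim 4 plans t-tests on programme costs that have no valid variance as described, and tests couple detection as a count with no stated denominator

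*Combined protocol and SAP*

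**What the plan says.** Section D, AIM 4, sets three hypotheses against clinic-based and community-based VCT. The first is a 30%-50% lower "program cost per client served associated with HIV testing and case detection". The second is more economically efficient case detection. The third is that "DDCP will detect substantial more (GT ~ 80%) serodiscordant couples than the alternatives".

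Costs are built by multiplying units of each resource by a price and summing. The output is stated as: "For each intervention and associated site we will estimate the total and average costs for the interventions". The test sentence then reads: "Analysis for this aim involves direct comparison across program types (independent t-tests for mean differences, and non-parametric tests for counts". It applies to cost, efficiency and the number of serodiscordant couples detected. No unit of observation, number of replicates, SD or denominator for couples is given. The section on precision and power has entries only for Aims 1 and 2.

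Other relevant text:
- **Measures, item (10) Cost:** "Cost data will include a range of costs for each item, with high, low, and average costs recorded". The list includes "average time clients spent with intervention", and benefits are to be discounted at 0%, 5% and 7%.
- **Section C:** the Project Accept team costed all components at two time points and "collected detailed individual intervention utilization data on all clients". The only testing volume given is 7,196 HIV tests.
- **Section B (Innovation) and Section E (Sources of Materials):** DDCP also collects utilization data for individuals at each use of a service.
- **AIM 4, on the comparator:** there are "highly detailed utilization data from Project Accept that specify associated rates of HIV case detection" and of couples' testing. A serodiscordant-couple count is not mentioned.
- **Sampling of Households:** recruitment continues by two routes, self-testing and the Care and Treatment Center (CTC), until 60 (up to 70) serodiscordant couples enrol, within 442 to 1,000 self-testing couples.

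**The concern.** A two-sample t-test needs independent observations within each group. A summed programme cost is a single figure, and dividing it by clients served gives a single average. High and low item prices describe uncertainty about inputs and do not create observations. If one average is applied to every client, the apparent sample size is large but the variance is artificial.

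A raw count of discordant couples depends on how many people a programme reached as well as on how well it finds such couples. Here reach is a design choice on the DDCP side and a historical fact on the comparator side. The 80% hypothesis could therefore be met or missed because of volume alone. The plan also leaves open what counts as detected. CTC recruits include a partner already known to be positive, and the qualitative sub-study reports about 40 serodiscordant couples who knew of the study and declined.

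**Working it through.** The plan gives no power or precision figure for Aim 4, so there is nothing to reproduce. The checks below use the plan's own numbers, with assumptions marked.

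**1. Degrees of freedom for the cost t-test** (pooled df = n1 + n2 - 2)
- One value per programme: 1 + 1 - 2 = 0. The statistic is undefined.
- One DDCP value against the two Project Accept costings: 1 + 2 - 2 = 1. The two-sided 5% critical value is t = 12.7, and Welch's version remains undefined. All the variance would come from two repeat costings of the comparator.
- Power in that second case, even if the two costings were treated as replicates: noncentrality = (reduction / CV) / sqrt(1/1 + 1/2). At an assumed CV of 10%, power is 15% for a 30% reduction and 25% for a 50% reduction. At an assumed CV of 30% it is 7% and 9%.
- A rank-sum test does no better. The smallest two-sided p is 1.0 for 1 against 1, and 2/3 = 0.67 for 1 against 2.

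**2. Effect of DDCP volume on the count** (illustration: all 60 couples come from self-testing, and enrolled couples stand in for tested couples)
- Constant yield: 60/442 = 13.6% (Wilson 95% CI 10.7-17.1). At 1,000 couples this gives 0.1357 x 1,000 = 136 couples, and 136/60 = 2.26.
- The hypothesised 1.8-fold count is reached at 442 x 1.8 = 796 couples (0.1357 x 796 = 108), with no change in yield.
- Constant count: 60/1,000 = 6.0% (4.7-7.6). The same 60 couples then conceal a 2.26-fold difference in yield.

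**3. Direction of the error**
- Against the only comparator volume stated, 7,196 tests (not split by VCT type), equal yield per person would give DDCP 884/7,196 = 0.12 to 2,000/7,196 = 0.28 of the comparator's count. Against a smaller comparator, the raw count would favour DDCP.
- With assumed counts of 60 against 33 (82% more), the rate ratio is (60/33) x (442/1,000) = 0.80 if DDCP reached 1,000 couples and the comparator 442. It is (60/33) x (1,000/442) = 4.11 if the reverse holds.

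**4. Whether a rate ratio would be informative** (assumed true ratio 1.8, 60 DDCP couples, counts treated as Poisson)
- Comparator rate treated as known: SE(log) = sqrt(1/60) = 0.129, so the 95% CI is 1.8 x exp(±1.96 x 0.129) = 1.4 to 2.3.
- Comparator of equal size, 60/1.8 = 33.3 couples: SE(log) = sqrt(1/60 + 1/33.3) = 0.216, so the 95% CI is 1.2 to 2.7.

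**The case against.** The best defence is that the plan is under-specified, not wrong. Individual utilization data exist for both programmes, and AIM 4 names micro-costing by units consumed, so client-level costs could be built and a t-test run on them. A test for counts could be a chi-square test of discordant against other couples, which carries a denominator. Cost per client served and Project Accept detection rates are already in the plan. Discounting at three rates is in substance a sensitivity analysis. The study is openly exploratory.

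Much of this stands. A reader might infer that no valid cost test is possible, that Aim 4 ignores denominators altogether, or that no sensitivity analysis is planned. The documents support none of these. What remains is narrower. No section says client-level costs will be built, and the one client-level input listed for costing is an average time. The use of the high and low item costs is unstated. The detection hypothesis and its outcome are both worded as a number of couples.

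A reader might also infer that the DDCP count is fixed at 60-70, or that the error favours DDCP. The target governs enrolment, not detection: every geographic cluster that is started is completed, and some known couples declined. Those decliners include couples identified at the CTC, so they do not show 40 extra self-test detections. Direction depends on comparator volumes that the documents do not give by VCT type.

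The constant-yield illustration has a limit too. The plan expects to enrol more couples because discordant ones prove harder to find, so 136 detections is not a forecast.

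**Conclusion.** The point holds. As described, the programme-level cost t-test has no valid variance: df is 0 with one value per programme and at most 1 with two comparator costings that are not independent. That rests on reading the costing output as AIM 4 states it, with one DDCP site.

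The couple-detection comparison cannot be interpreted without a denominator. DDCP's permitted volume range alone moves the count 2.26-fold at constant yield, against a hypothesised 1.8, and the error can run either way.

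The consequence is confined to Aim 4's cost, efficiency and couple-detection conclusions; Aims 1 to 3 are unaffected. The change should be made, because Aim 4 carries numerical hypotheses and Section B presents cost and efficiency as important for policy. Whether the 80% comparison can be rescued depends on Project Accept data that the documents do not describe.

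**What to change.** Rewrite the analysis paragraph of AIM 4.

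- **Cost:** replace the programme-level t-tests with cost per client tested, per HIV case detected and, where counts exist, per serodiscordant couple detected, all in one common price year. Give sensitivity ranges over the recorded high and low item costs, alongside the discounting at 0%, 5% and 7% already planned. Use a test on client-level costs only if such costs are actually built from utilization data in both programmes.
- **Detection, primary:** compare serodiscordant couples detected per person tested, as a rate ratio with 95% CI, separately against clinic-based and community-based VCT.
- **Detection, secondary:** report discordant couples per couple tested as a descriptive figure only. Section B argues that couples rarely test together under existing services, so conditioning on couples already tested removes the gain DDCP is meant to produce.
- **Definition:** count every couple detected by self-testing whether or not they enrol, and report CTC-recruited couples separately.
- **Feasibility check first:** confirm that Project Accept holds serodiscordant-couple counts by VCT type. If it does not, report DDCP yield with its CI and drop the 80% comparison.

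The cost is one rewritten paragraph and a check of existing variables. It needs no new participants, and the cost ranges use inputs already planned. The downside is that cost differences carry ranges instead of p-values, and the 80% comparison may have to be given up.
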